In summary, there is a great-unmet need for non-invasive treatments for chronic knee pain due to OA. In this proposal, we will test whether tDCS applied in conjunction with TUS is effective in treating chronic knee pain from OA.

Sponsors

This study is to be funded by the National Institutes of Health (Highland Instruments SBIR). Highland Instruments is a company focused on developing neurostimulation technologies for treatment of neural pathologies.

II. SPECIFIC AIMS

In this study, we aim to assess the effects of tDCS in combination with TUS for the treatment of pain and functional limitations in subjects with OA of the knee. We will explore *Aim 1 Sub-aims 1.1- 1.4* with a parallel design (active tDCS+ active TUS (n=32), and sham tDCS+sham TUS (n=32)). The specific aims of this experiment are as follows:

Aim 1: Assess the preliminary therapeutic effects of tDCS in conjunction with TUS in chronic OA knee pain.

Sub Aim 1.1: Safety of tDCS+TUS in subjects with OA of the knee.

We hypothesize that tDCS in conjunction with TUS can be applied safely in OA subjects. To test this we will implement a comprehensive battery of safety and neurological tests in OA subjects following fixed doses of tDCS in conjunction with TUS provided over [REDACTED] [REDACTED] for 10 days, 20 minutes/day. These assessments include EEG recordings, Visual Analog Mood Scale (VAMS), Mini Mental Status Exam (MMSE), 4-Choice Reaction Time, adverse events (AE) questionnaire and Neurological and physical examinations. We will compare active tDCS+ active TUS (n=32), and sham tDCS+sham TUS (n=32), inactive transducers. Follow-up evaluations will continue, while no further treatment is given, for 8 weeks (at 1, 2, 4, and 8 weeks) after the last stimulation.

Sub Aim 1.2 Effects of tDCS+TUS in pain perception in subjects with OA of the knee.

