We hypothesize that noninvasive tDCS in conjunction with TUS can be effective in decreasing the perception of pain in subjects with OA of the knee. To test this, we will use sensitive, currently validated outcomes for chronic pain subjects. A rater blind to the treatment arm will administer the following tests: Visual Analog Score (VAS) for Pain, Pain/Medication Diary, Von Frey assessment, and pain pressure tests (PPT) with algometer following stimulation detailed above, in SubAim 1.1. We will compare the stimulation conditions as above. Follow-up evaluations will continue, while no further treatment is given, for 8 weeks (at 1, 2, 4, and 8 weeks) after the last stimulation.

Sub Aim 1.3 Effects of tDCS+TUS in biomechanical function in subjects with OA of the knee.

We hypothesize that tDCS in conjunction with TUS can be effective in improving the biomechanical function in subjects with OA of the knee. To test this, we will compare the impact of active tDCS in conjunction with active TUS to the other stimulation conditions, as above, on markers of biomechanical function. We will use a biomechanical data acquisition and analysis system to specifically assess subject's knee biomechanical functionality and response to the intervention. For this purpose we will use a set of integrated sensors including accelerometers, gyroscopes, force sensors, and motion-capture cameras. Follow-up evaluations will continue, while no further treatment is given, for 8 weeks (at 1, 2, 4, and 8 weeks) after the last stimulation.

Sub Aim 1.4. Effects of tDCS+TUS in the quality of life in subjects with OA of the knee.

We hypothesize that tDCS in conjunction with TUS can be effective in improving the quality of life (QOL) in subjects with OA of the knee. To examine this aim, we will implement the Western Ontario and McMaster Universities Osteoarthritis Index (WOMAC), as this is recommended as one of the most sensitive and specific instruments for quality of life assessment in OA [68] and physical functioning assessment including a wide range of daily activities, such as bathing and getting in or out of the car. We will also use a generic health status measure - the Medical Outcomes Study 36-Item Short Form (SF-36) [68]. We will compare the stimulation conditions as above. Follow-up evaluations will continue, while no further treatment is given, for 8 weeks (at 1, 2, 4, and 8 weeks) after the last stimulation.

IV. SUBJECT SELECTION

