All analyses will be conducted according to the principle of intention-to-treat (using regression-based single imputation method). Intention-to-treat (ITT) population will include all randomized subjects. We will also perform an additional sensitivity analysis in which we will use the method of multiple imputation. The primary outcomes will be pain changes as indexed by VAS scores, biomechanical function changes as indexed with the motion analysis suite (i.e., our biomechanical data acquisition and analysis system), and QOL changes. Differences between the groups will be tested using Student's t-test, and additionally we will adjust for important baseline variables and test the time effect in general mixed longitudinal models. This model will be used for the primary and secondary outcomes (dependent variable (one model for each variable): VAS scores, biomechanical function changes as indexed with the motion analysis suite, and QOL changes, and independent variables will be treatment group and time of assessment (we will also adjust for baseline pain levels in this model)). Secondary analyses will be conducted in an exploratory manner (no correction for multiple comparisons). We will also conduct an EEG analysis to correlate EEG data with pain measures. Similar analysis will be conducted for the adverse effects measuring continuous outcome and for the categorical outcomes we will use Fisher's exact test. In both cases, for safety analysis we will use uncorrected p-value to increase the likelihood of detecting detrimental adverse effects.

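### Three primary outcomes are named with no success rule, multiplicity control or primary visit, and two of the three have no chosen variable

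*Combined protocol and SAP*

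**What the plan says.** **Primary outcomes.** Section VII (Biostatistical Analysis) reads "The primary outcomes will be pain changes as indexed by VAS scores, biomechanical function changes as indexed with the motion analysis suite", followed by QOL changes.

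**Analysis.** Group differences are tested by Student's t-test, "and additionally we will adjust for important baseline variables and test the time effect in general mixed longitudinal models". There is one model per outcome. Its "independent variables will be treatment group and time of assessment", with the note that "we will also adjust for baseline pain levels in this model".

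**Multiplicity.** There are two statements. One is "Secondary analyses will be conducted in an exploratory manner (no correction for multiple comparisons"); the other provides uncorrected p-values for safety. Neither covers the primary outcomes. No section gives an alpha, an any-one or all-three rule, an order of testing or a primary visit.

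**Aims.** Sub Aims 1.2 to 1.4 (Section II) carry separate hypotheses for pain, function and QOL. For function: "We hypothesize that tDCS in conjunction with TUS can be effective in improving the biomechanical function in subjects with OA of the knee". Section I closes with one question, about pain: "we will test whether tDCS applied in conjunction with TUS is effective in treating chronic knee pain from OA". Aim 1 describes the therapeutic effects to be assessed as preliminary.

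**Variables.** Section VI (Description of Assessments) records four tests with the motion suite: single-leg standing, step, functional reach, and Timed Up and Go. The last alone yields time, stride length and gait speed. For QOL, Sub Aim 1.4 puts WOMAC first because "this is recommended as one of the most sensitive and specific instruments for quality of life assessment in OA", and also uses SF-36. WOMAC has three components; SF-36 has eight concepts plus physical and mental indices.

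**Visits.** All three domains are measured at Visit 7 (stimulation day 5, mid-treatment, WOMAC without SF-36), Visit 12 (day 10, end of treatment) and Visits 13 to 16 (weeks 1, 2, 4 and 8 of follow-up).

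**The concern.** A primary analysis should be fixed to the point where two statisticians given the data would report the same result. Here they need not. For biomechanics and QOL they would have to choose the variable, and for all three outcomes the visit.

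The baseline also needs a choice. Visit 2 is called the baseline visit, but VAS and the full set of biomechanical tests are repeated before the first stimulation at Visit 3. On stimulation days VAS is taken both before and after the session, so naming Visit 7 or Visit 12 would still leave two pain readings.

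The success rule is open as well. With three primary results, a reader cannot tell whether one, two or three significant outcomes would mean that the treatment works. Under some rules the error stays at or below 5%; under one natural rule it does not.

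**Working it through.** **Inputs.** From the plan: three primary domains (Section VII), 32 per arm, planning effect size d = 0.9, and 0.72 as the largest effect in the cited OA guideline (Section VII, sample size). Assumed because the plan is silent: two-sided alpha 0.05 per test, equal correlation between the three outcomes (range 0 to 0.9), and one variable at one visit per domain.

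**1. The plan's own figure.** The plan says 32 per arm is enough for d = 0.9 but gives no alpha or power, so it cannot be reproduced exactly. For a t-test, the noncentrality is d√(n/2) = 0.9 × √16 = 3.6, with 62 degrees of freedom and critical value 1.999. Power is 94.3%. The statement is reasonable for one test at 0.05; the sample size is not the problem.

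**2. Any one of three counts as success, and nothing works.** With independent outcomes: 1 − 0.95³ = 14.3%. With common correlation ρ and c = 1.96:

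1 − ∫ φ(x) [Φ((c − √ρ·x)/√(1−ρ)) − Φ((−c − √ρ·x)/√(1−ρ))]³ dx

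| ρ | 0 | 0.3 | 0.5 | 0.7 | 0.9 |
|---|---|---|---|---|---|
| At least one false positive | 14.3% | 13.6% | 12.5% | 10.9% | 8.4% |

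Simulated t-tests with 32 per arm (200,000 trials) gave 14.3%, 13.7%, 12.5% and 11.1% for ρ = 0 to 0.7.

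**3. Pain truly improves, the other two do not.** The same formula with exponent 2 gives the chance that at least one of the other two is falsely declared: 9.8%, 9.5%, 9.1% and 8.4% at ρ = 0, 0.3, 0.5 and 0.7.

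**4. Other success rules.** If each sub-aim is claimed only on its own, each test has its own 5%. If all three must be significant, a false success requires a false rejection of at least one true null at 0.05, so the error is at most 5%. If nothing works it is 0.01% to 0.9% for ρ = 0 to 0.7.

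**5. If more than one variable or visit is tried.** The plan gives no count, so this is illustration only. Five uncorrected tests give 22.6% if independent and 18.3% at ρ = 0.5; ten give 40.1% and 28.7%.

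**6. Holm at overall 0.05.** If nothing works, the familywise error is 4.9%, 4.8%, 4.5% and 4.0% at ρ = 0, 0.3, 0.5 and 0.7. If only VAS has an effect (d = 0.9), it is 4.6%, 4.3% and 3.8% at ρ = 0.3, 0.5 and 0.7.

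**7. The mixed model.** The terms listed are group, time and baseline pain. With only these, the group coefficient is one difference averaged over visits, and biomechanics and QOL are not explicitly adjusted for their own baseline values.

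**The case against.** The strongest reply is that the plan never says one significant primary is enough. The sub-aims carry separate hypotheses, and separate claims need no joint correction. This stands, and it rules out a tempting inference: that the trial has a false-positive rate of 11% to 14%. That figure belongs to one possible rule only, and it falls below 11% once the correlation exceeds about 0.7.

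Second, the plan leans towards pain. The Section I question is about knee pain, randomization is stratified by VAS, and the planning effect sizes come from OA pain treatments. So one should not infer that a lone biomechanical or QOL result would be taken to answer that question. But Section VII gives pain no priority over the other two, and that mismatch is itself a reason to state the choice.

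Third, the study calls its effects preliminary, and how strict familywise control should be in a 64-subject trial is partly judgement. That is fair. It does not excuse leaving primary variables and visits open when Section VII itself separates primary from exploratory analyses.

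Fourth, some things are less open than they look. The word additionally makes the t-test read as the main test. The model terms come from a short list that does not expressly exclude a treatment-by-time term, and the important baseline variables could include each outcome's own baseline. These need confirming.

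Fifth, the schedule table is redacted and could define a suite score. Section VII shows no redaction, so the missing alpha, success rule and primary visit do not look like redaction effects.

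**Conclusion.** The point holds as a gap in specification that can affect the efficacy conclusion, and it should be closed before analysis. The missing success rule, multiplicity control and primary visit are certain from the text. The missing QOL score is nearly so: WOMAC is favoured, but none of its components is chosen. The missing biomechanical score is likely, subject to the redacted table.

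The gap in variable and visit needs no assumption about alpha or correlation. The 14.3% to 10.9% needs all of the following: two-sided 0.05, an any-one rule, no true effect, correlation 0 to 0.7, and one variable and visit per domain. It does not measure the freedom to choose among variables and visits, which would raise it.

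A reader might also infer that correction was waived for the primaries, or that selection after the fact is intended. The documents support neither: the waivers cover secondary and safety analyses, and on the primaries the plan is silent.

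**What to change.** Fix the wording in a document dated before anyone examines outcome data by arm. A date of unblinding will not serve, because the staff giving stimulation know the allocation throughout (Section VI, Blinding).

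**Preferred: keep three primaries.** Suggested text: *The primary endpoints are change from [Visit 2, or the pre-stimulation assessment at Visit 3] to [one named visit] in VAS pain, [one named motion-suite variable] and [one named WOMAC score]. Each is compared by two-sided t-test. Ordered p-values are tested by Holm at 0.0167, 0.025 and 0.05, overall two-sided alpha 0.05. The mixed model is supportive.* The baseline chosen must have all three measures: WOMAC is listed at Visit 2 but not before stimulation at Visit 3. If the named visit is a stimulation day, say whether the VAS before or after stimulation counts.

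**Alternative: one primary.** VAS pain change at one named visit, two-sided 0.05, with biomechanics and QOL secondary. This matches the Section I question.

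Requiring all three is also coherent, but it has about 1% power or less if only pain responds.

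**Mixed model, in either case.** Adjust each outcome for its own baseline as well as baseline pain, and state a treatment-by-time contrast at the named visit. If this model is to decide rather than the t-test, say so.

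**Cost.** No added patients. Power with 32 per arm:

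| | d = 0.9 | d = 0.72 |
|---|---|---|
| One test at 0.05 (single primary) | 94.3% | 80.9% |
| Holm, per outcome, all three effects equal to d | 91.6% to 93.5% | about 73% to 76% |
| Worst case for one outcome (0.05/3) | 86.9% | 66.2% |

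The Holm rows are simulated t-tests over correlations 0 to 0.7; at d = 0.72 the figure stays at about 75% to 76% up to 0.5. If only pain responds, Holm power for VAS is close to the worst case. The loss at 0.72 is real, and Section VII says smaller effects matter for some neurophysiological outcomes. The single-primary option avoids the loss for pain, but biomechanics and QOL then give up primary status.

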We will recruit up to 94 subjects for this study, with the intention of randomizing exactly 64 subjects with OA of the knee for this study. Once we randomize 64 subjects, we will stop recruiting subjects. Subjects will need to meet all of the following inclusion criteria and none of the following exclusion criteria:

Inclusion Criteria:

1. Able to provide informed consent to participate in the study.
2. Subjects between 18-85 years old.
3. Diagnosis of chronic osteoarthritis with pain of either knee as self-reported. *Prior to beginning baseline procedures this must be confirmed by medical records or a letter from the subject's physician, or diagnosis by a study staff licensed physician. This document may either be brought in by the subject or retrieved by study staff after the subject signs a medical release form. If the subject is unable to obtain the medical record, a diagnosis by a study staff licensed physician will be accepted. After consent, if the subject fails to provide the necessary documentation, or if it cannot be retrieved by study staff, the subject will be considered a screen fail.*
4. Existing knee pain of at least 3 on a 0-10 VAS scale on average over the past 6 months.
5. Pain of at least 3 on a 0-10 VAS scale on average over the week prior to the first stimulation session.
6. Pain resistant to common analgesics and medications for chronic pain used as initial pain management such as Tylenol, Aspirin, Ibuprofen, Soma, Parafon Forte DCS, Zanaflex, and Codeine.
7. Having the ability to feel pain as self-reported.

Exclusion Criteria:

1. Pregnancy or trying to become pregnant in the next 6 months.
2. History of alcohol or drug abuse within the past 6 months as self-reported.
3. Contraindications to transcranial brain stimulation or TUS, e.g. implanted brain medical devices or implanted brain metallic devices.
4. Unstable medical conditions (e.g. uncontrolled diabetes, uncompensated cardiac issues, heart failure or chronic obstructive pulmonary disease).
5. Epilepsy.
6. Use of carbamazepine within the past 6 months as self-reported.
7. Suffering from severe depression (with a score of >30 in the Beck Depression Inventory).
8. History of unexplained fainting spells as self-reported.

9. Head injury resulting in more than a momentary loss of consciousness.
10. History of neurosurgery as self-reported.

V. SUBJECT ENROLLMENT

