- Review inclusion and exclusion criteria.
- Obtain a signed and dated consent form.
- Conduct a Demographics Survey, Brief Medical History and the Beck Depression Inventory.
- Urine pregnancy exam (if applicable).

Confirmation of Osteoarthritis

Prior to the screening visit the subject will be asked if they can bring a document from their physician confirming the diagnosis of osteoarthritis of the knee. If the subject does not have it upon consenting, the subject will be asked to sign a medical release form allowing us to retrieve this document. If the subject is unable to obtain the medical record, a diagnosis by a study staff licensed physician will be accepted. This requirement has been outlined in the consent form. The baseline visit will only occur once confirmation of this diagnosis has been received.

Visit 2

Baseline Visit – (Approx Time: 2 hours)

This visit might be completed on the same day as the screening visit if time allows and the subject agrees.

Baseline assessments:

- Single Leg Standing Balance Test
- Step Test
- Functional Reach Test
- Timed Up and Go Test
- Knee Proprioceptive Test
- Knee Extensor/Flexor Force Test
- Knee Range of Motion (ROM)
- Visual Analogue Scale (VAS) for Pain

- Pain/Medication Diary
- Von-Frey Assessment
- Pain Pressure Test (PPT) with algometer
- Descending Noxious Inhibitory Control (DNIC)
- Western Ontario and McMaster Universities Osteoarthritis Index (WOMAC)
- Medical Outcomes Study 36-Item Short Form (SF-36)
- Visual Analog Mood Scale (VAMS)
- EEG recording
- Mini Mental Status Exam (MMSE)
- 4-Choice Reaction Time
- Neurological and Physical Exam

Visit 3

Re-screening procedure-(Approx Time: 5 minutes)

Prior to performing any assessments for visit 3, the subject will be re-screened to determine if they comply with the following inclusion and exclusion criteria: “*Pain of at least 3 on a 0-10 VAS scale on average over the week prior to the first stimulation session*”. If the subject does not report a VAS of at least 3 on a 0-10 VAS scale on average over the week prior to the stimulation session they will be screened-out of the trial and provided with the reason. If the subject does report a VAS of at least 3 on a 0-10 VAS scale on average over the week prior to the stimulation session, then they will continue with the remainder of the study visits.

1st Stimulation Visit – (Approx Time: 3.0 hours)

This study will be scheduled ~1 week after the baseline measurements were done.

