There will be 10 stimulation visits to be completed over 2 consecutive weeks (ideally Monday to Friday of each week). The subject will receive either 20 minutes of active tDCS in conjunction with active TUS, or sham tDCS in conjunction with sham TUS per day for the course of their stimulation visits.

Randomization:

Once eligibility and consent have been approved and completed, after all baseline evaluations and immediately before the first stimulation session, stratified blocked randomization will occur using the randomized list generated by an automatic web-based randomization program (www.randomization.com). A staff member who is not involved in any of the study procedures will be responsible for creating the randomization list and monitoring it during the study. Randomization will be stratified by baseline pain, using the median of Phase I as a cutoff (VAS of 7). Subjects will be randomly assigned to treatment or placebo groups in a 1:1 allocation ratio. We will use permuted blocks of variable sizes (4, 6, and 8) in a random manner to minimize the risk of study staff guessing at the next allocation. Randomization order will be kept in sealed envelopes.

Blinding:

All subjects and investigators will be blinded to the group assignment except for the co-investigators providing stimulation and staff involved in the randomization process (the latter would otherwise not be involved in study procedures). Only the staff involved in the randomization will be authorized to break the blind if there is a clinical need as requested by the PI, clinical care providers, Medical Monitor, or IMC. The patients will remain blinded until they have completed all visits (whether they complete all 16 visits or drop out early), or in the case of an adverse event necessitating un-blinding.

If the subject receives a sham stimulation, he/she may re-enroll into an open label portion of the study, where he/she will receive 10 days of active tDCS/TUS. Un-blinded co-investigators (e.g., who provided stimulation) will coordinate with subjects electing to enter into the open label phase, which will be conducted by the un-blinded study staff. The open-label study will be conducted without informing the blinded assessors of the patient enrollment. In the open label phase, we will complete the VAS assessments on Day 5 and Day 10 of stimulation. This collected data will not be analyzed with the main data collected in the study. This data will be used for exploratory analyses only.

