Before stimulation, the subject will complete a series of assessments:

- Single Leg Standing Balance Test
- Step Test
- Functional Reach Test
- Timed Up and Go Test
- Knee Proprioceptive Test
- Knee Extensor/Flexor Force Test
- Knee Range of Motion (ROM)
- Visual Analog Scale (VAS) for Pain
- Pain/Medication Diary will be given to the subject
- Von-Frey Assessment
- Pain Pressure Test (PPT) with algometer
- Descending Noxious Inhibitory Control (DNIC)
- Visual Analog Mood Scale (VAMS)
- Neurological and Physical Exam

After stimulation subjects will complete the following assessments:

- Visual Analog Scale (VAS) for Pain
- Von-Frey Assessment
- Pain Pressure Test (PPT) with algometer
- Visual Analog Mood Scale (VAMS)
- Descending Noxious Inhibitory Control (DNIC)
- Mini Mental Status Exam (MMSE)
- 4-Choice Reaction Time
- Adverse Events Questionnaire (AEs)

- EEG recording

Visits 4 – 6

Stimulation visits – (Approx Time: ¾ hour)

During the next 3 stimulation sessions – the subject will receive either 20 minutes of active tDCS in conjunction with active TUS, or sham tDCS in conjunction with sham TUS.

Pre-stimulation: immediately before stimulation, subjects will be asked to complete the following:

- Visual Analog Scale (VAS) for pain

After stimulation, the subject will complete a series of assessments:

- Visual Analog Scale (VAS) for Pain
- Visual Analog Mood Scale (VAMS)
- Mini Mental Status Exam (MMSE)
- 4-Choice Reaction Time
- Adverse Events Questionnaire (AEs)

Visit 7

5th Day of stimulation visits – (Approx Time: 2 ¼ hours)

Pre-stimulation: immediately before stimulation, subjects will be asked to complete the following:

- Visual Analog Scale (VAS) for pain

After stimulation subjects will complete the following assessments:

- Single Leg Standing Balance Test
- Step Test
- Functional Reach Test
- Timed Up and Go Test
- Knee Proprioceptive Test
- Knee Extensor/Flexor Force Test
- Knee Range of Motion (ROM)
- Visual Analog Scale (VAS) for Pain
- Pain/Medication Diary
- Von-Frey Assessment
- Pain Pressure Test (PPT) with algometer
- Descending Noxious Inhibitory Control (DNIC)
- Western Ontario and McMaster Universities Osteoarthritis Index (WOMAC)
- Visual Analog Mood Scale (VAMS)
- EEG recording
- Mini Mental Status Exam (MMSE)
- 4-Choice Reaction Time
- Adverse Events Questionnaire (AEs)

- Neurological and Physical Exam

Visits 8 – 11

6-9th Day of Stimulation visits – (Approx Time: ¾ hour)

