Pre-stimulation: immediately before stimulation, subjects will be asked to complete the following:

- Visual Analog Scale (VAS) for pain

After stimulation, the subject will complete a series of assessments:

- Visual Analog Scale (VAS) for Pain
- Visual Analog Mood Scale (VAMS)
- Mini Mental Status Exam (MMSE)
- 4-Choice Reaction Time
- Adverse Events Questionnaire (AEs)

Visit 12

10th Day of stimulation visits – (Approx Time: 2 ¼ hours)

Pre-stimulation: immediately before stimulation, subjects will be asked to complete the following:

- Visual Analog Scale (VAS) for pain

After stimulation subjects will complete the following assessments:

- Single Leg Standing Balance Test
- Step Test
- Functional Reach Test
- Timed Up and Go Test
- Knee Proprioceptive Test
- Knee Extensor/Flexor Force Test
- Knee Range of Motion (ROM)
- Visual Analog Scale (VAS) for Pain
- Pain/Medication Diary
- Von-Frey Assessment
- Pain Pressure Test (PPT) with algometer
- Descending Noxious Inhibitory Control (DNIC)
- Western Ontario and McMaster Universities Osteoarthritis Index (WOMAC)
- Medical Outcomes Study 36-Item Short Form (SF-36)
- Visual Analog Mood Scale (VAMS)
- EEG recording
- Mini Mental Status Exam (MMSE)
- 4-Choice Reaction Time
- Adverse Events Questionnaire (AEs)

- Neurological and Physical Exam

[figure not shown]
Visit 13, 14, 15, and 16

Follow-Up Visit – 1 week, 2 weeks, 4 weeks, and 8 weeks post-stimulation – (Approx Time: 2 hours)

These visits will be scheduled ~1, 2, 4, and 8 weeks after the last stimulation session and the following assessments will be performed:

- Single Leg Standing Balance Test
- Step Test
- Functional Reach Test
- Timed Up and Go Test
- Knee Proprioceptive Test
- Knee Extensor/Flexor Force Test
- Knee Range of Motion (ROM)
- Visual Analog Scale (VAS) for Pain
- Pain/Medication Diary
- Von-Frey Assessment
- Pain Pressure Test (PPT) with algometer
- Descending Noxious Inhibitory Control (DNIC)
- Western Ontario and McMaster Universities Osteoarthritis Index (WOMAC)
- Medical Outcomes Study 36-Item Short Form (SF-36)
- Visual Analog Mood Scale (VAMS)
- EEG recording
- Mini Mental Status Exam (MMSE)
- 4-Choice Reaction Time
- Adverse Events Questionnaire (AEs)
- Neurological and Physical Exam

Stimulation protocol: Subjects will be randomized to undergo one of two different treatment conditions: 10 sessions of sham tDCS/TUS, or 10 sessions of active anodal tDCS/TUS (32 subjects per study arm).

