For planning sample size calculation for this study, we utilized the OARSI recommendations for the management of knee OA. In this recommendation [84], a panel of experts reviewed evidence for the most commonly used pharmacological and non-pharmacological interventions for OA pain, giving effect sizes for all these interventions. Examples of non-pharmacological interventions are: education, physical therapy, aerobic exercise, knee brace, footwear, thermal modalities, TENS and acupuncture. Examples of pharmacological treatments are: acetaminophen, NSAIDs, injections with corticosteroids and treatment with glucosamine. In this review, effect sizes vary from 0.06 to 0.72. In fact the largest effect size was shown with injection of corticosteroids. Based on these effect sizes and the effect size we found in our pilot data (1.4), we set the effect size for our sample size calculation considering a effect size smaller or equal than our pilot data and larger than the

larger effect size from this meta-analysis (0.72) [84]. For this particular protocol, we plan a sample size of 64 participants. We considered the same sample per group as four times the subjects in Phase 1: 32 subjects per group. This will be enough to detect a difference in effect size of 0.9 and thus an effect size that is superior than other treatments used in OA according to a large guideline on OA management [84], though we expect a larger effect size for pain. However it is important to be able to detect significance with smaller effect sizes in the Phase 2 work, as some of the neurophysiological outcomes require additional power. Note that the main aim here would still be the comparison of active ESSstim vs. sham ESSstim.

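### Each primary change outcome gets a t-test and also an adjusted mixed model, with no statement of which decides; the model's only named covariate, baseline pain, is the outcome's own baseline for VAS alone.

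*Combined protocol and SAP*

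**What the plan says.** Section VII (Biostatistical Analysis) names three primary outcome domains, each worded as a change: VAS pain, function from the motion analysis suite, and QOL. For the comparison of arms it says: "Differences between the groups will be tested using Student's t-test, and additionally we will adjust for important baseline variables", the adjustment being made in mixed longitudinal models. It then says that the model serves the primary and secondary outcomes, one model per variable, and gives the terms: "independent variables will be treatment group and time of assessment (we will also adjust for baseline pain levels in this model"). No arm-by-time term is named, the further baseline variables are not listed, and no time point is given for the t-test.

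Other sections bear on this:
- **Section VI, Randomization:** "Randomization will be stratified by baseline pain, using the median of Phase I as a cutoff (VAS of 7").
- **Section IV, inclusion criterion 5,** sets a floor on entry pain: "Pain of at least 3 on a 0-10 VAS scale on average over the week prior to the first stimulation session".
- **Section VI, Visit 2 (baseline)** includes VAS, seven functional tests, "Western Ontario and McMaster Universities Osteoarthritis Index (WOMAC") and SF-36.
- **Section VI, Visit 3:** "Before stimulation, the subject will complete a series of assessments". That list repeats VAS and all seven functional tests, but not WOMAC or SF-36.
- **Section VI, follow-up:** "These visits will be scheduled ~1, 2, 4, and 8 weeks after the last stimulation session", in addition to assessments during treatment.
- **Section VII, sample size,** on 32 per group: "This will be enough to detect a difference in effect size of 0.9".

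**The concern.** Two analyses are planned for each primary outcome, and the text points both ways on which leads. The word introducing the model suggests that the t-test comes first. The next sentence assigns the model to the primary outcomes. Nothing says what follows if they disagree.

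The choice affects efficiency. A change-score t-test removes the own baseline by plain subtraction, which is usually less precise than regression on that baseline, and it does not use the stratification factor. If the model decides with baseline pain as its only covariate, VAS is adjusted for its own baseline, but function and QOL are adjusted for a different variable. Their own baselines are collected, but whether they are among the unlisted variables cannot be told.

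If either test could count as the result, there is also some room for selection.

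**Working it through.** **The plan's own figure.** The sample-size text gives 32 per group and an effect size of 0.9, without alpha, sidedness or power, so it cannot be formally reproduced. Assuming two-sided 0.05, the noncentrality is 0.9 × √(32/2) = 3.60, and the t-test with 62 df has 94% power. The claim that 32 is enough is therefore consistent. At 0.72, the largest effect in the guideline that the plan cites, noncentrality is 0.72 × 4 = 2.88 and power is 81%.

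**Assumptions not in the documents.** Two-sided 0.05; effect d in SDs of the change score; follow-up SD 1 and baseline SD k; correlation r between an outcome's baseline and follow-up; correlation c of 0.3 or 0.5 between baseline pain and the own baseline of a non-pain outcome, with pain related to follow-up only through that own baseline; complete data at one time point.

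**Own-baseline adjustment.**
- Variance of the change score: 1 + k² − 2rk.
- Variance after regression on the own baseline: 1 − r².
- Ratio: (1 − r²)/(1 + k² − 2rk), which is (1 + r)/2 at k = 1.

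Example with k = 1 and r = 0.5: the change variance is 1 + 1 − 1 = 1.00, the adjusted variance is 0.75 and the ratio is 0.75. The effect of 0.72 becomes 0.72/√0.75 = 0.83, and power with 60 df is 91%.

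| k | r | variance ratio | power at 0.72 | power at 0.9 |
|---|---|---|---|---|
| t-test on change | – | 1 | 81% | 94% |
| 1 | 0.3 / 0.5 / 0.7 | 0.65 / 0.75 / 0.85 | 94 / 91 / 87% | 99 / 98 / 97% |
| 0.7-0.8 | 0.3 | 0.78-0.85 | 87-89% | 97-98% |
| 0.7-0.8 | 0.5 | 0.89-0.95 | 83-85% | 95-96% |
| 0.7-0.8 | 0.7 | 0.98-1.00 | 81-82% | 94-95% |

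The rows with k below 1 matter for VAS, because the entry floor of 3 may make the baseline SD smaller than the follow-up SD. At k = 0.7 and r = 0.7 the ratio is 0.51/0.51 = 1.00, so nothing is gained.

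**Baseline pain as the only covariate for function or QOL.** The ratio is 1 − c²(r − k)²/(1 + k² − 2rk). The most favourable case shown (c = 0.5, k = 1, r = 0.3) gives 1 − 0.25 × 0.49/1.40 = 0.91. Across the settings the ratio is 0.91-1.00 and power at 0.72 is 81-84% (61 df), so little is recovered.

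**Type I error.** This was simulated with 20,000 null trials per setting: 64 subjects, blocks of 4, 6 and 8 within two pain strata.
- The VAS t-test alone, with equal strata, rejects in 2.7 / 3.2 / 4.2% of trials at k = 1 for r = 0.3 / 0.5 / 0.7. At k = 0.7-0.8 the figures are 3.6-4.0 / 4.4-4.6 / 5.1-5.2%. It is at worst conservative.
- If either test could count at the same time point, the error is 5.5-6.1% for VAS. For a non-pain outcome it is 5.2-5.7% with pain-only adjustment and 5.6-7.8% if the model includes the own baseline.

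**The case against.** The strongest reply is that nothing here is invalid and little is at stake. The outcomes are changes, so the own baseline already enters by subtraction. Both analyses are sound in a randomized trial. The ordinary sense of the sentence is that the t-test leads and the model supports it. Baseline pain is the stratification factor, so adjusting every model for it is defensible. At the design effect of 0.9 the t-test already has 94% power. The larger gains need an effect of 0.72, which the plan uses as a value to exceed rather than as its target, and they depend on assumed r and k.

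Most of this stands, and it limits the point to efficiency and clarity. It does not remove the point: the plan never says which analysis decides, the covariates remain unlisted, and the sample-size text itself wants power for smaller effects, though it ties this to neurophysiological outcomes.

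Three stronger readings are tempting and are not supported:
- **That baseline function and QOL are ignored.** They enter through the change score and may be among the unlisted covariates.
- **That the comparison is biased or its error rate materially inflated.** Each test alone is valid, and inflation needs a choice made after seeing results.
- **That the error reaches about 7-8% or more for this reason.** Simulated values of 6.6-8.4% arise when a Day 10 t-test competes with the model's visit-averaged effect, and 8.6-8.8% under another set of assumptions. They come from the missing time point, which is a separate gap.

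**Conclusion.** The concern holds as a matter of efficiency and prespecification. Section VII leaves the deciding analysis open and names the own baseline as a covariate for VAS only. Under the stated assumptions, own-baseline adjustment adds about 6 to 13 percentage points of power at an effect of 0.72 when the SDs are equal (87 − 81 to 94 − 81). It adds 0 to 8 points when the baseline SD is 0.7-0.8 of the follow-up SD, and 0 to 5 points at 0.9. Adjusting function or QOL for baseline pain alone adds at most 3 points at 0.72. Selection between the two tests at one time point is a small risk. No trial-specific loss can be given, because the documents supply neither the correlations nor the SDs. The change should be made because it is nearly free, not because the planned tests are wrong.

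**What to change.** Name the baseline-adjusted mixed model as the deciding test for each primary outcome, at one named contrast or time point, with an arm-by-time term if that is a single visit. Replace the open reference to baseline variables with a list: the outcome's own continuous pre-treatment baseline, and baseline pain or its VAS 7 stratum. For VAS, baseline pain is the own baseline. Label the t-test supportive.

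State which baseline is used. VAS and the functional tests are measured at Visit 2 and again before stimulation at Visit 3, so one must be chosen for each. For WOMAC and SF-36, use Visit 2, the only pre-treatment visit that lists them.

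The cost is SAP wording and one or two degrees of freedom, with no new data collection. The motion-suite metric and the QOL instrument that count as primary must be named first, because their baselines cannot be coded until then.
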